3.8 Training and Procedures Required to use VR101

No medical or surgical intervention or clinician involvement is required to use VR101 safely and effectively. VR101 is designed to be self-inserted by users of the device and remain in place for up to 7 consecutive days. After 7 days, the ring is removed by the user, discarded, and, at the user's discretion, replaced with a fresh VR101 ring.

VR101 is intended to be available as an over-the-counter (OTC) product that will not require healthcare professional assistance or supervision for use. The user will not be assisted with use of the device. As such, the user must be able to insert and remove the device solely based on reading the provided instructions for use (IFU) and labeling. All applicable warnings, precautions and contraindications are listed on the IFU.

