13.3 Anticipated Adverse Device Effects (ADE)

Following is a list of adverse events that may be related to the use of VR101 or the sham:

- Device-related discomfort/pain

J3 Bioscience, Inc.	Clinical Investigation Plan and Protocol CI03	CI03-CIP Rev. 02 Page 49 of 60
	A Clinical Investigation to Evaluate Efficacy of the J3 Bioscience Lubricating Intravaginal Ring VR101 as a Personal Lubricant Device in Women	

- Device-related cramping
- Device-related vaginal itching/burning/irritation
- Device-related non-menstrual bleeding
- Toxic-shock syndrome
- Ring adherence to the vaginal wall
- Inability of user to remove the ring
- Bowel obstruction
- Ring breakage that causes injury
- Device-related infection
- Device-related vaginal/cervical/urethral irritation/inflammation
- Device-related malodor
- Device-related vaginal discharge (e.g., excessive lubrication / secretions)
- Device-related incontinence
- Intermittent Nausea
- Intermittent Headache
- Physical interference with other intravaginal or intrauterine devices

Some anticipated ADEs listed above are hypothetical, and some have been observed clinically. Refer to reports for CI01 and CI02 for a complete list of observed ADEs (either definitely or potentially related to VR101 use) and their frequency.

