13.4 Device Deficiencies

Following is a list of device deficiencies that may be related to failure of VR101 or sham to meet its acceptance criteria:

- Outer polymeric ring is damaged - no release of contents
- Outer polymeric ring is damaged - release of contents
- Ring weld fails - no release of contents
- Ring weld fails - release of contents
- Device has rough surfaces
- Device will not stay in place
- Device is contaminated (on removal from package, extraneous matter is observed)
- Device is too rigid
- Device is too soft
- Device is too large
- Device is too small
- Device is too slippery
- Device cannot be easily inserted
- Device cannot be easily removed
- Instructions are missing and/or hard to follow
- Packaging is difficult to open
- Device is not biocompatible

J3 Bioscience, Inc.	Clinical Investigation Plan and Protocol CI03	CI03-CIP Rev. 02 Page 50 of 60
	A Clinical Investigation to Evaluate Efficacy of the J3 Bioscience Lubricating Intravaginal Ring VR101 as a Personal Lubricant Device in Women	

Per the Clinical Hazard Assessment, the residual risks associated with the above device deficiencies are adequately mitigated and/or are outweighed by the potential Clinical Benefits of VR101.

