10.0 Acceptable Suppliers

NOTE: SUPPLIER IDENTIFICATION IS FOR J3B USE ONLY (NOT TO BE DISTRIBUTED TO SUPPLIERS). Acceptable suppliers are to be identified on the last (separate) page of the Part Specification. This page is not to be used or referenced when obtaining quotes from potential suppliers or copied to existing suppliers.

J3 Bioscience, Inc. For INTERNAL USE ONLY	Labeling Specification SUPPLIER IDENTIFICATION	LBL 001 Rev. 01 Page 5 of 5
---	---	-----------------------------------

Acceptable Suppliers

Any supplier of Avery Products

J3 Bioscience, Inc.
For INTERNAL USE
ONLY

Labeling Specification
SUPPLIER IDENTIFICATION

LBL 002
Rev. 01
Page 1 of 5

REVISION LOG

Rev	Eff. Date	CO	Brief Description of Change	Author
00	17-03-31	2017-06	Original approval and implementation	pT
01	21-01-2020	CR-0005	
 Updated Study Contact Numbers from CI02 to CI03 Corrected to reflect non-collection of used rings per CI03 CIP R01 	JTC

Distribution List

- Document Control**
- R and D**
- Manufacturing**
- Quality Assurance**
- Regulatory**
- Clinical**
- Cust. Svc/ Purchasing**
- Management**
- Lubrizol/ Vesta**
- Purchasing**

Control Status of This Document:

Controlled

Document must be marked as Original, Controlled, Uncontrolled or Draft

J3 Bioscience, Inc. For INTERNAL USE ONLY
	
Labeling Specification SUPPLIER IDENTIFICATION
	
LBL 002 Rev. 01 Page 2 of 5

--	---	--

1.0 Part Number LBL 002

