2.0 Name VR101 Instructions for use- for devices used in clinical investigations

3.0 Description

IFU (Instructions for Use) to be affixed to or accompany VR101 devices used in CI 02.

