4.0 General Requirements

4.1 Color: black lettering/graphics on white label

4.2 Description, Label Dimensions, and Graphics (markings) per following table:

Product Code	Description & Label Size	Graphic
LBL 001	
IFU printed on either standard white paper or on white paper with pressure-sensitive adhesive backing. Preferred Dimensions are 8.5 x 11"
 
Other dimensions are acceptable, as long as print is \geq 8 pt font.
	See Next Page for text of IFU

VR101 Insertion Instructions

Prior to use, inspect each package for damage.

Do not use if package or device appears damaged.

Read ALL Instructions before inserting and removing VR101.

1. Wash and dry your hands thoroughly.
2. Remove ring from its pouch.
3. Before inserting VR101, find a position that is comfortable. You can insert the ring while lying down, squatting, or standing with one leg up, whatever position is most comfortable for you.
4. Hold the ring between your thumb and first finger, pressing opposite sides of the ring together. You may want to twist it into a figure 8.
5. It may help you to hold open the folds of skin around your vagina with your opposite hand while inserting the ring.
6. Place the tip of the ring in the vaginal opening and then push the folded ring gently into your vagina. Push the ring up and toward your back. Do not use any lubrication.
7. If you feel any discomfort, the ring probably is not inserted far enough. Try gently pushing the ring further into your vagina. The ring will not get lost in your body.
8. When you are finished, wash and dry your hands thoroughly.

Return any rings that you were unable to place for any reason to the clinic at your next visit.

Before returning a ring to the clinic, place in the original foil-lined pouch if available. If not, place in a zip lock-type bag.

Warnings:

- Do not use the ring if it appears to be damaged and/or if the package appears open or damaged.
- Do not re-insert a ring that you removed or that was expelled if it appears damaged or contaminated. You may wash it in clean water and re-insert it if it is clean.

VR101 Removal Instructions

Remove each VR101 ring after 7 days of use.

1. Wash and dry your hands.
2. Choose the position that is most comfortable for you.
3. Put you index finger into your vagina and hook it through the ring and gently pull downward and forward to remove the ring.
4. Discard the used ring in the trash and out of reach of children and pets. Do not flush the ring in the toilet.

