5. Insert a new ring after removal of the used ring, according to the instructions provided above.

Warning: Do not re-insert a ring that you removed or that was expelled if it appears damaged or contaminated. You may wash it in clean water and re-insert it if it is clean. Or, use a new ring. Return any rings that were unable to be replaced to the clinic during your next visit.

If you have any questions or concerns call the study coordinator:

In Utah: [contact]

In Idaho: [contact]

J3 Bioscience, Inc. For INTERNAL USE ONLY	Labeling Specification SUPPLIER IDENTIFICATION	LBL 002 Rev. 01 Page 4 of 5
---	---	-----------------------------------

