J3 Bioscience, Inc.	Title: Clinical Hazard Assessment VR101	Doc. #: CHA 01 Rev: 00
------------------------	---	------------------------------

Hazards Associated with use of VR101, and Verification or Validation that Hazards are Acceptably Mitigated to Justify placing VR101 on the market			
Hazardous Condition	Potential Effect	Mitigation Method/ Verification that Method has been Implemented	Verification or Validation that Potential Hazards are Reduced to Acceptable Levels and Users are Adequately Informed of Residual Risks
VR101 is difficult to remove	Device is a foreign body that can induce infection	
Mechanical tests to assess device compressibility (STP-004.) The physical dimensions of the device are not significantly different from other currently marketed IVRs.
 
Biocompatibility of VR101 device.
	
Results of mechanical tests to assess device compressibility (See R02-A) demonstrate the compressibility of the device meets specs and is comparable to that of clinically acceptable devices.
 
Biocompatibility test results demonstrate risks associated with a retained ring are low and acceptable (See Gad Consulting Services Report “Biological Safety Assessment of VR101 Lubricating Intravaginal Ring”, dated 18 January 2019)
 
During CI02, 6 of 72 participants had difficulty removing the ring.
 
Residual Risk: IFU contains the following Warning: “Some women may find VR101 difficult to remove. If VR101 removal is difficult, a partner may assist. If removal by a partner is difficult, not possible, or painful, contact your healthcare provider for assistance.”

Conclusions

1. All identified risks have been reduced as far as possible and residual risks have been identified to end users in the provided labeling.
2. Review of the benefits derived by use of VR101 and the risks inherent in its use results in a conclusion that the benefits of device use outweigh the risks inherent in anticipated end-use and misuse situations.

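### Appendix C says the IFU warns that the ring may be hard to remove, but the study IFU and pouch label in Appendix B carry no such warning

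*Protocol*

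**What the plan says.** Protocol section 3.8 sets the standard for the instructions: "the user must be able to insert and remove the device solely based on reading the provided instructions for use (IFU) and labeling". It adds that the IFU lists all applicable warnings, precautions and contraindications. Section 5.6 places the labeling in Appendix B.

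The removal steps in the Appendix B IFU (LBL 002 Rev. 01) give technique only: "hook it through the ring and gently pull downward and forward to remove the ring". The one warning beside them concerns putting a damaged or contaminated ring back in. The sheet ends with a general line: "If you have any questions or concerns call the study coordinator". The pouch label (LBL 001 Rev. 01) says nothing about removal.

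Appendix C has a row for a ring that is difficult to remove, and names infection from a retained foreign body as the potential effect. The row reports six of 72 CI02 participants with difficulty and gives the residual risk as "IFU contains the following Warning: “Some women may find VR101 difficult to remove". It then says that a partner may help and that a healthcare provider should be contacted if that fails or hurts. Appendix C concludes that users have been told of the residual risks in the labeling.

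The body of the protocol recognizes the hazard. Section 13.3 lists "Inability of user to remove the ring" among the anticipated device effects. Section 13.4 lists "Device cannot be easily removed" among the deficiencies and points to the hazard assessment for the judgment that the residual risk is acceptable.

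**The concern.** CI03 uses the hazard assessment as its own risk-benefit support (sections 7.2, 7.3 and 13.4). For difficult removal, the only disclosure to users that the assessment cites is an IFU warning. The IFU attached to the same protocol does not have it.

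Participants exchange rings at home on days 7, 14 and 21. A woman whose ring will not come out finds the technique on her sheet, but not that this is a known difficulty, that a partner may help, or when to seek care. The sheet does say what to do with a ring that could not be placed; it has no counterpart for one that cannot be removed. What is at stake is patient information, not the validity of the efficacy result.

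**Working it through.** No sample-size or power figure is involved. The check is a comparison of texts, followed by a rough sense of scale.

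**1. Side by side.**
- Appendix C: some women may have difficulty; a partner may assist; contact a provider if that is difficult, impossible or painful.
- Appendix B IFU: removal technique, disposal, insertion of the next ring, reinsertion warning, coordinator number. Difficulty, partner help and provider contact for removal are all absent.
- Appendix B pouch label: the nearest text concerns irritation. Removal is absent.

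**2. Is the Appendix B text complete?** Its cover gives 11 pages. Cover 1 + LBL 001 5 + LBL 002 5 = 11. The IFU wording is printed in full, so the absence is not a redaction or a lost figure.

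**3. Order of events.** The hazard assessment took effect on 25 March 2019. LBL 002 was revised to Rev. 01 on 21 January 2020. That revision log has two entries: "Updated Study Contact Numbers from CI02 to CI03" and a correction about not collecting used rings. The warning could have been added then.

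**4. How common was difficulty in CI02?** Input: 6 of 72 women (Appendix C).
- Proportion: 6/72 = 8.3%.
- Exact (Clopper-Pearson) 95% limits: lower = 0.025 quantile of Beta(6, 67) = 3.1%; upper = 0.975 quantile of Beta(7, 66) = 17.3%.

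**5. What might that mean for CI03?** The documents do not say how the difficulty arises, so here are two separate assumptions.
- *Fixed trait of the woman.* 160 × 8.33% = 13.3, so about 13 of the 160 planned women (limits 160 × 3.12% = 5.0 and 160 × 17.26% = 27.6).
- *Constant risk per ring, one event per affected woman.* CI02 used 890 + 275 = 1,165 rings (Appendix C), or 1,165/72 = 16.2 per woman. 6/1,165 = 0.515% (exact 95% CI 0.189% to 1.118%). Scheduled home removals in the blinded phase are 3 × 160 = 480, which gives 480 × 0.515% = 2.5 (0.9 to 5.4). Extension rings would add to this.

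The first figure counts women and the second counts removals. Neither counts harms that a warning would prevent.

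**The case against.** The strongest reply is that Appendix C may describe a different IFU. Its tables are headed as justification for placing the device on the market, its release controls refer to the marketplace, and one labeling entry is in the future tense. Its warning sends users to their own healthcare provider, whereas the study IFU sends them to the coordinator. Of ten distinct labeling statements it cites, only three can be found in the readable text of Appendix B, which is what one would expect if other labeling were meant. Section 3.8 is itself written partly about the intended over-the-counter product. This stands: a reader might infer that the protocol flatly contradicts itself, and the documents do not establish that. It does not supply the missing advice, and section 7.3 adopts Appendix C for this trial without saying which IFU it describes.

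A reader might also infer that the warning is the only control. It is not. The same row relies on compressibility testing, dimensions similar to those of marketed rings, and biocompatibility results, and it judges the risk of a retained ring low.

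The trial has further safeguards. Calls on days 7, 14 and 21 ask about help with removal (section 5.4.4), the day-28 ring is removed at the clinic visit, and the coordinator can be called. Section 6.2 reports no serious device effects in CI01 or CI02. The consent form was not available and may cover removal. All of this stands and keeps the point small.

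Finally, a reader might infer a threat to the per-protocol set, because SAP 7.3 requires independent removal. That is not supported. SAP 7.3 already states the requirement and sends other deviations to blind review, SAP 10.5 reports the assignments made, and the nine major violations in SAP Table 1 are lubricant use (7) and oral sex (2).

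**Conclusion.** The point holds as a minor patient-safety labeling improvement, something to consider rather than a defect in the design. The study IFU and pouch label lack a removal warning that the hazard assessment attributes to the IFU. That is certain from the printed text. Whether it is also a contradiction depends on which IFU Appendix C means, and the documents leave that open.

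The firm figure for scale is the CI02 one: 8.3% of women (exact 95% CI 3.1% to 17.3%), severity not given. The projections to CI03 rest on assumptions that the documents cannot test. Their limits should not be joined into one range, because they come from different models and count different things. The conclusion is limited to the IFU and label. The primary endpoint, analysis sets, sample size and blinding are unaffected.

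**What to change.** Add the removal-difficulty warning already drafted in Appendix C to LBL 002, together with the study contact so that events reach the site and are recorded. Use the same text for VR101 and sham, since section 5.6 requires identical instructions. State in section 7.3 whether Appendix C describes the study IFU or a commercial one. The clinical wording is for the sponsor and investigators.

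The cost is a revision of the plan and label with sponsor and IRB approval (section 10), one reprinted sheet, and site training if the change counts as procedural (section 13.11). SAP Rev. 00 (sections 1 and 10.1) reports data collection complete, so the label change can no longer reach CI03 participants and serves only further use of this IFU. The sentence in section 7.3 would still clarify the record for CI03.

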### LIST OF ABBREVIATIONS AND DEFINITIONS

ADE	Adverse Device Event (Effect)
AE	Adverse Event
CFR	Code of Federal Regulations
CIP	Clinical Investigation Plan
CI01	Clinical Investigation 01 (Pilot)
CI02	Clinical Investigation 02 (Pivotal)
CI03	Clinical Investigation 03 (Supplemental)
CRA	Clinical Research Associate
CRF	Case Report Form
FDA	Food and Drug Administration of United States
GCP	Good Clinical Practice
IB	Investigator's Brochure
ICF	Informed Consent Form
ICH	International Conference on Harmonization
IDE	Investigational Device Exemption
IRB	Institutional Review Board
ISO	International Organization for Standardization
IVR	Intravaginal Ring
NSR	Non-Significant Risk
OHRP	Office of Human Research Protection
PI	Principal Investigator
SADE	Serious Adverse Device Event (Effect)
SAE	Serious Adverse Event
SAP	Statistical Analysis Plan
SOP	Standard Operating Procedure
USAE	Unanticipated Serious Adverse Event

J3 Bioscience, Inc.	Statistical Analysis Plan	CI03-SAP Rev. 00 Page 6 of 31
	CI03: A Clinical Investigation to Evaluate Efficacy of the J3 Bioscience Lubricating Intravaginal Ring VR101 as a Personal Lubricant Device in Women	

## 1 INTRODUCTION

This document describes the planned statistical analyses for Protocol CI03 CIP “**CI03: A Clinical Investigation to Evaluate Efficacy of the J3 Bioscience Lubricating Intravaginal Ring VR101 as a Personal Lubricant Device in Women.**” This analysis plan is meant to supplement the study protocol. Any deviations from this analysis plan will be described in the final clinical study report. In this revision (00), Section 10 describes the procedures and outcomes of the blind data review following all data collection and resulting revisions and additions to the original statistical analysis plan.

### 1.1 Purpose of the analyses

The data from CI03 will be used to support submission of a premarket 510(k) notification to the FDA to enable regulatory clearance of the device in the United States (US). The investigation and data analyses are designed to comply with the requirements of ICH E6, ICH E9, and with guidance from ICH E9 (R1), allowing the investigation to also support regulatory submissions and registrations in other countries or regions. The investigation is designed to demonstrate the efficacy of the VR101 lubricating intravaginal ring (IVR) as a personal lubricant device, for vaginal application. The device is intended to moisturize and lubricate, to enhance the ease and comfort of intimate sexual activity and supplement the body's natural lubrication.

### 1.2 Study Design

This is a randomized, double-blind, sham-controlled, 4-week parallel group study with an optional 2-week open-label extension and 1-week safety follow-up. Participants will be randomized (1:1) into two groups for the study. One group will be assigned to use the active VR101 vaginal lubrication device and the other group will be assigned to use a sham ring that does not contain lubricant. The study is designed as a two-center trial with approximately equal enrollment at each site.

### 1.3 Number of participants

A minimum of 160 females will be randomized to VR101 or sham ring during the 4-week treatment phase of the study.

### 1.4 Diagnosis and Key Inclusion Criteria for the study population

[figure not shown]
Sexually active women at least 21 years of age who report experiencing lack of vaginal lubrication during sexual intercourse will be screened for participation in the study. The key inclusion criteria are:

J3 Bioscience, Inc.	Statistical Analysis Plan	CI03-SAP Rev. 00 Page 7 of 31
	CI03: A Clinical Investigation to Evaluate Efficacy of the J3 Bioscience Lubricating Intravaginal Ring VR101 as a Personal Lubricant Device in Women	

- Responses on the Female Sexual Function Index (FSFI) Lubrication Domain indicating dysfunctional level of vaginal lubrication during sexual intercourse.
- Willingness to comply with the study schedule, abstain from use of vaginal moisturizers, lubricants, lubricated condoms, other vaginally placed devices, and hormone replacement therapy, use of an approved method of contraception if appropriate, and attempt sexual intercourse at least 4 times during the 4-week treatment period.
- Ability to place and remove the IVR appropriately and independently.

A complete listing of inclusion and exclusion criteria is included in the CI03 Study Protocol effective January 31, 2020.

## 1.5 Study Schematic

## 1.6 Summary of Study Schedule

- After each participant has read and signed the Informed Consent document and has met all inclusion and exclusion criteria, she will be randomized into either the VR101 device or sham ring group. A four-week supply of assigned devices will be provided to each participant.
- Participants will be instructed to use the randomly assigned device continuously and exchange with a new device every 7 days.
- Study staff will complete a follow-up call with participants on the 7th, 14th and 21st day following randomization to remind them to remove their device and insert a new one. During each call, information about compliance, including changes in

J3 Bioscience, Inc.	Statistical Analysis Plan	CI03-SAP Rev. 00 Page 8 of 31
	CI03: A Clinical Investigation to Evaluate Efficacy of the J3 Bioscience Lubricating Intravaginal Ring VR101 as a Personal Lubricant Device in Women	

medications, use of lubrication products, frequency of sexual intercourse and oral sex and any health or issues they are having with the study device will be collected.

- Participants will return for a final study visit (Visit 2) on day 28 (+/-2 days). Participants will discontinue use of their device during the 28-day Visit and will return all unused devices. They will complete the Visit 2 FSFI at that time.
- Participants who complete the Visit 2 assessment will be offered two VR101 devices in a 2-week open label extension, followed by a final safety follow-up phone call 1 week after the end of the open label extension.

